8.1.3.2 Secondary Efficacy Analysis

Secondary Analysis of the Primary Efficacy Variables

ANCOVA analyses will be carried out on change from baseline to final NMSS total score and change from baseline to final PDSS-2 total score. The ANCOVA model will contain treatment and country as the main effects and baseline score as the covariate.

Sensitivity analyses will be carried out on the above variables with the same ANCOVA model using all randomized subjects. In this analysis, Baseline Observation Carried Forward (BOCF) will be applied to subjects who do not have post-randomization assessment of NMSS or PDSS-2.

Key Secondary Efficacy Variables

Key secondary endpoints will consist of the following validated scales:

- UPDRS Part II score
- CGI-C
- PDQ-8 summary index

The 3 key secondary variables will be analyzed with the same MMRM model as the primary analysis. For the analysis on CGI-C, the scores collected at the visits will be the dependent variable.

If both primary efficacy variables are statistically significant after adjusting for multiplicity, the Stepwise Gatekeeping Procedure will be utilized and the 3 key secondary endpoints will be tested using the Hochberg procedure with significance level of 0.05.

Other Secondary Efficacy Variables

Other secondary endpoints include:

- NMSS domain scores
- PDSS-2 domain scores
- UPDRS total score, Part I score, Part III score, Part IV score
- Parkinson Anxiety Scale (PAS) total and subscale scores
- King's PD Pain Scale total and domain scores

These variables will be analyzed with the same MMRM model as the primary analysis. For the analysis on PGIC, the scores collected at the visits will be the dependent variable.

8.1.4 Safety Analysis

All safety analysis will be performed on the safety dataset unless otherwise specified. Comparisons between LCIG and OMT groups will be performed with two-sided test at the significance level of 0.05.

Unless otherwise specified, the treatment group differences in continuous safety variables (e.g., change from baseline to final observation on laboratory tests) will be assessed using an ANOVA model with the term of treatment, and the treatment group differences in binary safety variables will be evaluated using a Fisher's exact test.

8.1.4.1 OMT and LCIG Study Drug Exposure

The duration of OMT exposure will be calculated for each subject as the date of the last visit minus the date of randomization. The duration of LCIG study drug exposure will be calculated for each subject as the date of the last dose of LCIG study drug minus the date of the first dose of LCIG study drug plus 1. The duration of OMT and LCIG study drug exposure will be summarized with descriptive statistics (number of subjects with non-missing data, mean, standard deviation, median, minimum and maximum).

8.1.4.2 Adverse Events

Adverse events will be coded using the most current version of the Medical Dictionary for Regulatory Activities (MedDRA). Adverse events will be summarized by primary MedDRA system organ class (SOC) and preferred term (PT). Subjects reporting more than one adverse event for a given MedDRA PT will be counted only once for that term. Subjects reporting more than one adverse event within an SOC will be counted only once for the SOC total. Subjects reporting more than one adverse event will be counted only once in the overall adverse event total.

Each adverse event will be categorized by severity (mild, moderate, severe) and by relationship to study treatment (reasonable possibility, or no reasonable possibility). Detailed search criteria for adverse events of special interest (AESIs) will be defined in a SAP prior to database lock.

A treatment-emergent adverse event (TEAE) is defined as:

- For OMT group: any adverse event that begins or worsens in severity the day after randomization and within 30 days following the last visit.
- For the LCIG group: any adverse event that begins or worsens in severity from the day of the initial device placement (NJ or PEG-J) through Week 26 Visit for those subjects continuing to LCIG commercial treatment, or through 30 days after final device removal for those subjects not continuing LCIG commercial treatment.

A summary of the number and percentage of subjects will be prepared for the following:

- TEAEs
- TE Serious AEs (including deaths)
- TEAEs leading to premature discontinuation of treatment
- TEAEs by maximum relationship to study drug
- TEAEs by maximum severity
- Treatment-emergent AESIs

Serious adverse events with onset during the Screening Period for all subjects screened, adverse events and serious adverse events with onset after day of randomization and before day of initial device placement for the LCIG group, as well as adverse events during the transition period for LCIG subjects continuing LCIG commercial treatment will also be summarized.

8.1.4.3 Clinical Laboratory Variables

For each continuous clinical laboratory variable, analyses of the mean change from baseline to each scheduled visit and to the minimum, maximum and final value will be presented by treatment group.

Clinical laboratory observations will be categorized as normal, low, or high relative to the reference (normal) range associated with the laboratory that performed the assay. For each clinical laboratory variable with a reference range, shift tables will be prepared for reference range category shifts from baseline to minimum, maximum and final value.

Criteria for potentially clinically significant (PCS) values will be pre-specified for selected laboratory variables in an SAP prior to database lock. For each variable, a summary of the number and percentage of subjects who have at least one post-baseline observation that meets the PCS criteria and is more extreme than their baseline value will be provided.

8.1.4.4 Vital Sign Variables and Weight

For each vital sign and weight variable, analyses of the mean change from baseline to each scheduled visit and to the final value will be presented by treatment group. For this analysis, the average of multiple observations on the same day will be calculated and treated as the observation for the day. For LCIG subjects' visits with multiple observations scheduled on the same day, the post-infusion change from the day's pre-infusion baseline will be summarized for each scheduled time point.

Criteria for potentially clinically significant (PCS) values will be pre-specified for selected vital sign and weight variables prior to database lock. For each variable, a summary of the number and percentage of subjects who have at least one post-baseline observation that meets the PCS criteria and is more extreme than their baseline value will be provided.

8.1.4.5 ECG Variables

For each ECG variable, analyses of the mean change from baseline to each scheduled visit and to the final value will be presented by treatment group. For this analysis, the average of multiple observations on the same day will be calculated and treated as the observation for the day. For LCIG subjects' visits with multiple observations scheduled on the same day, the post-infusion change from the day's pre-infusion baseline will be summarized for each scheduled time point.

Criteria for potentially clinically significant (PCS) values will be pre-specified for selected ECG variables prior to database lock. For each variable, a summary of the number and percentage of subjects who have at least one post-baseline observation that meets the PCS criteria and is more extreme than their baseline value will be provided.

8.1.4.6 Additional Safety Variables

The following additional summaries of safety measures will be prepared.

- The responses to the MIDI
- The responses to the C-SSRS
- The responses to the Sleep Attacks Questionnaire
- Percent of subjects who are cognitive impaired (MoCA score \leq 26)

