Abnormal Vitamin B₁₂ of questionable clinical significance (indeterminate or low normal results at screening) require MMA and homocysteine laboratory assessments be reviewed for determination of B₁₂ deficiency prior to entry into the study. Only labs at Visit 1 are exclusionary. If at any time during the study a subject displays symptoms of polyneuropathy, the Investigator must perform this lab panel and any other assessment that the Investigator feels is appropriate for further evaluation of polyneuropathy symptoms. Thyroid function tests will be done at Visit 1 only.

Pregnancy Testing

- WOCBP must have a negative serum/urine pregnancy test result at Screening, and a negative serum/urine pregnancy test at Study Day 1. Monthly pregnancy

testing should be performed during treatment, including at the last dose and until $5 \times$ the half-life of the AbbVie product.

- Subjects with borderline pregnancy tests at Screening must have a serum pregnancy test ≥ 3 days later to document continued lack of a positive result.
- Females of non-childbearing potential (either postmenopausal or permanently surgically sterile as defined above) at Screening do not require pregnancy testing at any time.

Montreal Cognitive Assessment (MoCA)

The MoCA has been widely utilized in clinical settings to study cognition in PD. It was originally developed as a screening tool to assess mild cognitive impairment in the general population. The MoCA will be administered to assess for cognitive impairment and will be administered at Visits 3, 6, 7 and 8. The scale assesses seven cognitive domains, including visuospatial/executive, naming, memory/delayed recall, attention, language, abstraction and orientation. The maximum total score that can be obtained is 30 and a cut off score of 25/26 on MoCA has demonstrated a diagnostic sensitivity of 90% for individuals diagnosed with mild cognitive impairment. Additionally the movement disorder society has recommended the use of this scale due to its acceptable clinimetric properties⁴⁵ and diagnostic utility.

Minnesota Impulsive Disorders Interview (MIDI)

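### The MoCA is planned only as the percentage of subjects at or below a cut, with no change-from-baseline analysis, and the SAP contains no MoCA analysis at all

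*Protocol*

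**What the plan says.** Protocol 5.3.1.1 describes the scale and its timing: "The maximum total score that can be obtained is 30 and a cut off score of 25/26 on MoCA" is cited for detecting mild cognitive impairment, and "The MoCA will be administered to assess for cognitive impairment and will be administered at Visits 3, 6, 7 and 8". Visit 3 is the baseline visit; Visits 6, 7 and 8 are Weeks 6, 12 and 26. The MMSE is given at Visit 1 only, so the MoCA is the only cognitive test repeated on treatment.

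Protocol 8.1.4.6 lists the MoCA among additional safety summaries as "Percent of subjects who are cognitive impaired", with impairment defined as a score of 26 or less. It names no visit, change score, shift or baseline adjustment.

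Protocol 8.1.4 sets the general defaults. "Comparisons between LCIG and OMT groups will be performed with two-sided test at the significance level of 0.05". Unless otherwise specified, continuous safety variables get an ANOVA with treatment as the only term, with change from baseline to final observation as its example, and "the treatment group differences in binary safety variables will be evaluated using a Fisher's exact test". Other numerical safety measures are handled on their own scale, arm by arm. One example is Protocol 8.1.4.5: "For each ECG variable, analyses of the mean change from baseline to each scheduled visit and to the final value will be presented".

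In the SAP the MoCA appears only as a row of the Appendix A schedule. It is absent from the safety measures (4.6), the derived datasets (6.7) and every subsection of the safety analysis (10.1 to 10.8). SAP 12.0 nevertheless states that the analysis is unchanged from Protocol Amendment 4.

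**The concern.** Cutting a 30-point score at one value discards most of what it measures, and a percentage at a visit does not use the subject's own starting point. Some consequences follow from the definition alone. A subject at 26 or below at baseline can fall any distance without being counted. A fall from 30 to 27 is invisible. A subject stable at 25 counts the same as one who fell from 29 to 25.

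The protocol protects its other safety data against this. Laboratory values, vital signs and ECG get mean changes from baseline, and even their threshold summaries count only values more extreme than the subject's own baseline (8.1.4.3 to 8.1.4.5). The MoCA gets neither.

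The default ANOVA for continuous safety variables does not clearly fill the gap. It applies unless otherwise specified, the MoCA is specified as a percentage, and the MoCA is in neither list of safety variables (Protocol 5.3.4, SAP 4.6). At stake is how much a finding of similar percentages in the two arms would reassure anyone about cognition on treatment.

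**Working it through.** **1. The plan's own power figure.** Protocol 8.2 gives 90% power with 37 evaluable subjects per group, and 90% with 44 per group when 10% have baseline carried forward. Its inputs are differences of 24.8 − 8.2 = 16.6 (SD 24) on NMSS and 13.1 − 4.3 = 8.8 (SD 12.2) on PDSS-2, correlation 0.5, and Hochberg at two-sided 0.05. Simulation gives 90.3% and 90.5%, so the figures reproduce. They concern the primary endpoints only; the documents state no effect, SD, mean, correlation or power for the MoCA.

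**2. Assumed MoCA inputs.** 40 per arm (44 less 10% is 39.6); integer scores capped at 30; SD 3; baseline mean 24.5 to 26; baseline-to-Week 26 correlation r of 0.5 to 0.7; true between-arm difference 1.5 points; two-sided 0.05.

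**3. Share who cannot register a decline.** A score of 26 or less corresponds to a value below 26.5 before rounding, so the share is Φ((26.5 − mean)/SD).
- Mean 24.5: Φ(2.0/3) = Φ(0.667) = 75%
- Mean 26: Φ(0.5/3) = Φ(0.167) = 57%
- Mean 27, outside the assumed range: Φ(−0.5/3) = Φ(−0.167) = 43%

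**4. Closed-form check** (1.5 points, SD 3, r = 0.7, 40 per arm).
- *Baseline-adjusted score:* residual SD = 3 × √(1 − 0.49) = 2.14; SE = 2.14 × √(2/40) = 0.479; power = Φ(1.5/0.479 − 1.96) = Φ(1.17) = 88%. For 80% power, 33 per arm are needed.
- *Change score, no covariate:* SD = 3 × √(2 × 0.3) = 2.32; SE = 0.520; power = Φ(1.5/0.520 − 1.96) = Φ(0.93) = 82%.
- *Percentage at or below 26:* at mean 25.5 the Week 26 percentages are about 63% and 80%. A pooled z-test has 39% power and needs 110 per arm for 80%. Fisher's exact test is lower still (step 5).

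**5. Simulation** with rounding and the cap at 30.

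| Setting (40 per arm) | Fisher on ≤ 26 | ANOVA on change | ANCOVA with baseline |
|---|---|---|---|
| Mean 25.5, SD 3, r 0.7, 1.5 points | 28% | 80% | 85% |
| Mean 25.5, SD 3, r 0.5, 1.5 points | 29% | 60% | 71% |
| Mean 24.5-26, SD 3, r 0.5-0.7, 1.5 points | 23-32% | 58-81% | 69-86% |
| Mean 25.5, SD 3.5, r 0.5, 1 point | 11% | 22% | 28% |

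Moving the cut to 25 or less in the first row raises Fisher's power only to 34%, so the loss comes mainly from cutting, not from the choice of cut.

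**6. Sensitivity.** At mean 25.5, over SD 2.5-3.5, r 0.5-0.8 and differences of 1-2 points, Fisher ranges over 11-64% and ANCOVA over 28-100%. For a 1-point difference at SD 3.5-4 and r 0.5, the gain from ANCOVA is only about 12-17 points, and both analyses are underpowered. ANCOVA was higher than Fisher in every setting tried. These runs used one post-baseline visit; a repeated-measures model was not simulated.

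**The case against.** The bullet is a descriptive summary and names no test. The MIDI, C-SSRS and sleep-attack items listed beside it become counts and percentages in the SAP, and SAP 10.8 rules out arm comparisons for the C-SSRS. Fisher's test reaches the MoCA only through the general default, so its power is an imperfect measure of harm. This stands: the power figures show how much information the cut loses; they do not describe a named test. The loss remains for a descriptive reader, because a crude percentage still hides decline.

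A reader might infer that the plan ignores baseline. The documents do not go that far: no visit is named, and nothing prevents showing the baseline percentage beside the later ones. What is missing is a within-subject or baseline-adjusted comparison.

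A reader might also infer that the trial is blind to cognition. It is not. The NMSS mood/cognition and attention/memory domains and UPDRS Part I are analysed with the baseline-adjusted MMRM (Protocol 8.1.3.2, SAP 9.3), and adverse events are collected. These are not repeated cognitive tests, but they give some information.

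Nor do the documents present cognitive decline as an expected risk. It is not an adverse event of special interest, no cognitive term appears in the table of common adverse events (Protocol 3.2), the MoCA is in no objective, and subjects with MMSE below 24 are excluded. This limits the importance of the point. It does not explain why a score collected four times should be reduced to a percentage and then left out of the SAP.

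**Conclusion.** The concern holds as a minor safety-analysis point. Two facts need no assumption: the protocol's only MoCA summary is a percentage with no change or baseline adjustment specified, and the SAP has no MoCA analysis despite saying that nothing changed. That the cut hides declines below 26 and within 27 to 30 follows from its definition.

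The size rests wholly on assumed MoCA values. In the settings of step 2, moving from the cut to the baseline-adjusted score raises power from roughly a quarter to a third up to roughly 70-85%. Much of that gain comes from using the change score at all; baseline adjustment adds the rest. The gap should not be read as a fixed figure, since it narrows for small effects and larger SDs. Only its direction was constant.

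Nothing here touches the primary or key secondary conclusions, and the documents do not support saying that the trial would miss a cognitive harm. The supportable statement is that similar percentages at or below 26 would be weak evidence of no change in the MoCA.

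**What to change.** In Protocol 8.1.4.6, and in a new subsection of SAP section 10, add change from baseline in MoCA total score at Weeks 6, 12 and 26 by arm on the Safety Dataset, with the between-arm difference and 95% CI. Adjust for baseline, either by ANCOVA at each visit or with the existing MMRM. If the MMRM is used, take its terms from Protocol 8.1.3.1, which include treatment-by-visit; SAP 9.2 does not list that term. At minimum, apply the trial's own ANOVA on change for continuous safety variables.

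Keep the percentage at or below the cut as a descriptive baseline-to-visit shift table, so that new impairment is separated from impairment present at entry. Add the MoCA to SAP 4.6 and 6.7 so that the data reach the analysis.

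The cost is a small protocol and SAP edit and one or two tables. The scores are already collected at every visit needed, so no new visits, raters or subjects are required.

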8.1.5 Interim Analysis

No interim analysis is planned for this study.

8.2 Determination of Sample Size

Approximately 88 subjects will be enrolled into the study and randomized in a 1:1 ratio to either optimized medical treatment or LCIG. There are no results on NMSS or PDSS-2 available from randomized trials comparing LCIG and OMT. Interim data from ongoing Phase 3b Study M12-920 showed that the improvement in NMSS total score from baseline to Week 12 is 24.8 in the LCIG group with standard deviation of 24. Results from Zibetti et al (2013) showed that the improvement in PDSS-2 total score after an average of 3.5 months of LCIG treatment was 13.1. The standard deviation was not provided and is estimated to be 12.2 assuming the correlation between baseline and follow-up visits is 0.5.

The significance level for this study is 0.05. For sample size determination, it is assumed that the improvement in the OMT group is 33% of the LCIG group, i.e., the improvement is 8.2 on NMSS total score and 4.3 on PDSS-2 total score, and that the correlation between these 2 measures is 0.5. Simulation showed that a study with 37 subjects per group will have 90% power to declare statistical significance on at least one of these 2 alternative primary endpoints after multiplicity adjustment using Hochberg procedure. It is further assumed that 10% of randomized subjects in either treatment group will not provide post-randomization efficacy assessment. Additional simulations showed that 44 subjects per group will provide 90% power in the sensitivity analysis using baseline observation carried forward for subjects without post-randomization assessment. Therefore the total planned enrollment is decided to be 88 subjects.

8.3 Randomization Methods

Approximately 88 subjects will be enrolled into the study and randomized in a 1:1 ratio to either optimized medical treatment or LCIG at the end of Visit 3. Subject randomization will be stratified by country.

9.0 Ethics

9.1 Independent Ethics Committee (IEC) or Institutional Review Board (IRB)

Good Clinical Practice (GCP) requires that the clinical protocol, any protocol amendments, the Investigator's Brochure, the informed consent and all other forms of subject information related to the study (e.g., advertisements used to recruit subjects) and any other necessary documents be reviewed by an IEC/IRB. The IEC/IRB will review the ethical, scientific and medical appropriateness of the study before it is conducted. IEC/IRB approval of the protocol, informed consent and subject information and/or advertising, as relevant, will be obtained prior to the authorization of drug shipment to a study site.

Any amendments to the protocol will require IEC/IRB approval prior to implementation of any changes made to the study design. The investigator will be required to submit, maintain and archive study essential documents according to ICH GCP and all other applicable regulatory requirements.

Any serious adverse events that meet the reporting criteria, as dictated by local regulations, will be reported to both responsible Ethics Committees and Regulatory Agencies, as required by local regulations. During the conduct of the study, the investigator should promptly provide written reports (e.g., ICH Expedited Reports, and any additional reports required by local regulations) to the IEC/IRB of any changes that affect the conduct of the study and/or increase the risk to subjects. Written documentation of the submission to the IEC/IRB should also be provided to AbbVie.

9.2 Ethical Conduct of the Study

The study will be conducted in accordance with the protocol, International Conference on Harmonization (ICH) guidelines, applicable regulations and guidelines governing clinical study conduct and the ethical principles that have their origin in the Declaration of Helsinki. Responsibilities of the clinical investigator are specified in [Appendix A](#).

9.3 Subject Information and Consent

The investigator or his/her representative will explain the nature of the study to the subject, and answer all questions regarding this study. Prior to any study-related screening procedures being performed on the subject, the informed consent statement will be reviewed and signed and dated by the subject, the person who administered the informed consent, and any other signatories according to local requirements. A copy of the informed consent form will be given to the subject and the original will be placed in the subject's medical record. An entry must also be made in the subject's dated source documents to confirm that informed consent was obtained prior to any study-related procedures and that the subject received a signed copy.

Information regarding incentives for subjects and information regarding provisions for treating and/or compensating subjects who are harmed as a consequence of participation in the study can be found in the informed consent form.

